### 4.3 Safety Endpoint

- Immediate and short term response as assessed by the investigator following treatment, defined as type and intensity of response and the time it takes for it to subside.
- Any adverse events associated with various setting(s) used during the treatment and follow-upperiod.

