## 7.2.4.2 Level of improvement and satisfaction

Subject's Improvement and Satisfaction with treatment will be recorded by using the GAI scale at the last follow up visit (see Appendix B).

Table 1 - Clinical Evaluation Tools

Claim/task	When to conduct?	Tool		
Photography	Baseline, immediately before	Standardized digital photographs		
	treatments 2, 3, FU 3			
Vaginal pH	Baseline, immediately before	Standard pH paper		
	treatments 2, 3, FU 3			
Histopathology & Molecular	Baseline, immediately before	Histology slides, special staining		
Studies	treatments 2, 3, FU 3	and assays.		
Immediate and short term	Immediately following treatments	Examination of skin in the treated		
response evaluation by	1-3	area based on 5 level scale		
investigator		(Appendix F)		
Subject's duration of post-	Before treatments 2, 3, FU 3	Subject Questionnaire on post		
treatment adverse events questionnaire		treatment response (Appendix G)		
Subjects discomfort/pain	Immediately following treatments	VAS (Appendix E)		
assessment	1-3			
Subjects improvement/	FU3.	GAI (see Appendix B)		
satisfaction assessment				
score				
Independent reviewers score	At the end of the study	GAI (see Appendix B)		

Confidential 11

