## 9 Adverse Events

#### 9.1 Adverse Events Definitions

In this study, an Adverse Event (AE) is any undesirable clinical occurrence (sign, symptom, illness, or other medical event), that appears or worsens during the clinical study, or requires medical treatment or intervention to a subject, whether it is considered to be device-related or not. If an adverse event occurs, the first concern will be the safety and welfare of the patient. Appropriate medical intervention will be made.

Any AE or complication reported by the patient or observed by the physician that occurs during or after treatment with the device will be recorded in the medical record or source document and on the Case Report Form (CRF). The investigator will determine if the AEs are device-related or procedure-related. This assessment shall include the onset date, resolution date, severity, seriousness, frequency, treatment and outcome.

Each AE should be assessed according to the following criteria:

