#### 9.1.6 Anticipated Outcome Related Adverse Events

Anticipated adverse events in this study include pain, tenderness, purpura, persistent erythema, edema, burn, blistering, crusting, hyperpigmentation, hypopigmentation, scarring and potential for damage to hair follicles within the treatment area and subsequent loss of hair within the treatment area.

Any anticipated AE that occurs at any time during or after the use of the study device must be recorded by the Investigator. If the anticipated AE, in the opinion of the Investigator, is likely to affect the safety of the subjects or the conduct of the study, the ethic committee will be notified of the effect within 10 working days. In this study if an adverse event occurs the Investigator will continue following the subject until the case is resolved or up to 1 month following the last visit, whichever comes first.

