## 9.1.7 Unanticipated Adverse Device Effects

In the event of a serious (or unanticipated) adverse event, the Investigator will immediately notify the study monitor by telephone. If such an adverse event is being reported after normal working hours, the Investigator will leave a voice message with accompanying report of the AE.

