## 12.7 Appendix G – Subject Duration of Post Treatment Adverse Events Questionnaire

Check one of the following boxes to indicate today's Treatment/Follow up Visit:  Tx2  Tx3 FU3.							
Please check the box that correlates with the duration of possible post treatment side effects by checking the box that corresponds to the day your symptoms resolved:							
	Day of the Treatment	1 day after	2 day after	3 day after	4 day after	7 day after	
Redness							
Swelling							
Crusting							
Blistering							

Confidential 27

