## 12.7 Appendix I – Additional Safety Background Data

Non-ablative or non-burning RF therapy has been used for vaginal tightening previously within human vaginal mucosa at 75-90 J/m2. (J Sex Med 2010 Sep; 7(9): 3088). For the purpose of this study premenopausal patients will be treated at 90J/m2, whereas the post menopausal patients will be treated with less cumulative heat. We have calculated that the thickness of vagina epithelium (the most susceptible tissue to thermal injury) is decreased 16% in menopause. (This has been calculated by the percent change seen in human vaginal epithelium of menopausal versus non-menopausal on histomorphometry measurements -J. Sex Med 2009 Nov 6(11): 3097.) Reducing energy delivery by 16% yields a safe basement level of 75.6 J/m2 for menopausal patients. Again it is important to emphasize the proposed study device has thermal feedback safety settings and real-time multipolar thermal control to virtually eliminate the possibility of tissue burns. Additionally, now over 3 patients have been treated in Geneva Switzerland with [name], using the proposed study device (Venus Versa) both internally intravaginal and externally. No burns or off target damage was appreciated.

On advisement from the IRB committee and combined with the above information update; for further patient protection we will modify the protocol to perform initial safety parameters on the first 10 patients using 75J/m2 for premenopausal patients and 90J/m2 for premenopausal patients. If these safety parameters are consistent with the preliminary safety studies in Europe, the IRB will review these results, at which time we will submit an expanded study of up to 300 for review.

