#### SAFETY SOP FOR POTENTIAL BURNS:

The following SOP shall be conformed to at all study facilities if a patient experienced any first, second or third degree burn or pain beyond narcotics:

- 1. The event will be reported to the study Director within 24 hours of occurrence.
- 2. A copy of the patient chart and treatment parameters are to be forwarded to the study Director within 24 hours.
- 3. Immediate triage and treatment of the patient shall be determined by the treating physician and based upon severity and type of burn identified.
- 4. The study Director will be responsible for issuing a written report to the company and the IRB Chairman no later than 7 days from the incident.
- 5. Long term follow up and care shall continue at the discretion of the treating physician.
- 6. All patients experiencing a complication of the device will be followed a minimum of 2 years following the initial injury. Longer care and observation will be at the discretion of the treating physician.
- 7. All minor complications such as appearance or altered sensation, except for pain, can be reported within 30 days of patient complaint. Both chart and treatment parameters are to be provided to the study Director and shared with the company and IRB chairman.

Confidential 30

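### The 30-day limit for reporting minor complications exceeds the four-week treatment interval and is not reconciled with section 9.1.7, and Appendix G cannot record altered sensation or any effect lasting beyond day 7

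*Combined protocol and SAP*

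**What the plan says.** **Reporting.** The burn SOP in Appendix I ends with item 7: "All minor complications such as appearance or altered sensation, except for pain, can be reported within 30 days of patient complaint". The chart and treatment parameters then go to the study Director and are shared with the company and the IRB chairman.

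Two other rules cover some of the same events. For an anticipated event that the investigator thinks likely to affect safety or study conduct, section 9.1.6 says "the ethic committee will be notified of the effect within 10 working days". Section 9.1.7 says: "In the event of a serious (or unanticipated) adverse event, the Investigator will immediately notify the study monitor by telephone". The anticipated list in section 9.1.6 does not name altered sensation.

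Appendix I also plans a safety look at the first 10 subjects, after which "the IRB will review these results, at which time we will submit an expanded study of up to 300 for review". It gives no data cut-off for that look.

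**Duration.** Section 4.3 includes among the safety endpoints the early response to treatment, "defined as type and intensity of response and the time it takes for it to subside". Appendix F grades that response immediately and at about 30 minutes. Appendix G asks the subject about later duration by "checking the box that corresponds to the day your symptoms resolved". Table 1 schedules it "Before treatments 2, 3, FU 3". Its rows are redness, swelling, crusting and blistering. Its columns are the day of treatment and days 1, 2, 3, 4 and 7.

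**The concern.** Energy may be raised from one session to the next (section 7.5, step 1). A reporting limit longer than the gap between sessions means that people outside the site may first hear of a complaint after the subject has been treated again. For altered sensation there is also a direct conflict: one section can be read as requiring a telephone call at once, while another allows 30 days.

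The form raises a different problem. A subject still red on day 20, or numb at any time, has no correct box to tick. She leaves the line blank or ticks a day that is too early, and either answer makes the reaction look shorter or absent in the data meant to describe its duration.

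**Working it through.** **1. Deadline against next treatment.** Inputs: limit of 30 days from complaint (item 7); visits four weeks apart (Appendix A), so Tx1 on day 0, Tx2 on day 28, Tx3 on day 56.

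For a complaint c days after a treatment, the latest permitted report is day c + 30 and the next treatment is day 28. Overrun = c + 30 − 28 = c + 2 days.

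- c = 0: 2 days after the next treatment.
- c = 27: 29 days after it.
- Raised at the Tx2 visit itself (day 28): the limit runs to day 58, past Tx3 on day 56.

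So all 28 complaint days (0 to 27) have a deadline after the next treatment. Two of the three sessions are followed by another, so this covers 2 × 10 = 20 of the 30 sessions planned in ten subjects.

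Section 7.1 calls the interval approximate and gives no window for Tx2 or Tx3. Varying it, as an assumption:

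| Interval (days) | Complaint days with deadline after next treatment |
|---|---|
| 21 | 21 of 21 |
| 28 | 28 of 28 |
| 31 | 29 of 31 |
| 35 | 29 of 35 |

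A shorter fixed limit would only partly help. At a 28-day interval, 14 days falls before the next treatment for complaints up to day 13, and 7 days for complaints up to day 20. Tying the deadline to the next treatment closes the gap fully.

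**2. The three rules side by side.**

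| Rule | Trigger | Deadline | Recipient |
|---|---|---|---|
| Section 9.1.6 | Anticipated AE thought likely to affect safety or conduct | 10 working days | Ethics committee |
| Section 9.1.7 | Serious or unanticipated AE | Immediate | Study monitor |
| SOP item 7 | Minor complication other than pain; altered sensation named | 30 days from complaint | Study Director, company, IRB chairman |

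Altered sensation is absent from the 9.1.6 list, so it can be read as unanticipated and fall under 9.1.7. It is also named in item 7. The recipients differ as well, and no text ranks the rules.

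**3. Appendix G.** Boxes exist for days 0, 1, 2, 3, 4 and 7, which is 6 days. A form completed at day 28 covers days 0 to 28, which is 29 days. Days with no box: 29 − 6 = 23, namely days 5 and 6 (2) and days 8 to 28 (21).

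FU3 has a window of ± seven days. Taking the earliest as 28 − 7 = 21 and the latest as 30 + 7 = 37 days after Tx3, the days beyond day 7 with no box number 21 − 7 = 14 to 37 − 7 = 30. Adding days 5 and 6 gives 16 to 32.

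There is no box for an unresolved effect and no row for sensation. Appendix H, question 3, asks about sensations only while treatment is being given.

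**The case against.** Much can be said for the plan.

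- **Recording at the site.** Section 9.1 puts "Any AE or complication reported by the patient or observed by the physician that occurs during or after treatment with the device" into the source record and onto the CRF, with onset and resolution dates. Appendix A schedules AE recording at all four visits. Section 9.1.6 follows events until resolution or one month after the last visit, and SOP item 6 follows any subject with a device complication for at least two years. This stands. A reader might infer that altered sensation or long-lasting effects go unrecorded, or that the investigator would re-treat unaware. The documents do not support either.
- **No hold step.** Item 7 gives its recipients no approval or stopping role before the next treatment; the site sets the energy. This stands, and limits the consequence to oversight.
- **Scope.** The SOP's opening sentence confines it to subjects with a burn or pain beyond narcotics. If that governs item 7, the main event in those subjects has already gone to the study Director within 24 hours (items 1 and 2), with a written report to the company and IRB chairman within 7 days (item 4). This is a possible reading. But item 7 speaks of all minor complications and its examples are not burns, so its scope needs stating.
- **Endpoint.** The section 4.3 response is investigator-assessed, and section 7.6.1 expects reactions to last a few hours. That is fair, but section 7.2.1 pairs the investigator's grading with the subject's duration questionnaire, and Appendix F stops at about 30 minutes. Time to subside after that comes from Appendix G or from whatever the site enters as an AE. Section 7.5 calls transient erythema and edema the normal response, so not every reaction need be entered.

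**Conclusion.** Two defects hold. Item 7 permits a delay that runs past the next treatment for every complaint day at the nominal interval, and it is not reconciled with section 9.1.7. Appendix G truncates subject-reported duration and omits altered sensation.

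The size is minor. The 2 or more days are latest permitted dates, not expected delays, and assume a 28-day interval; an interval above 30 days would remove the overrun for the earliest complaints only. CRF dates partly back up the duration data.

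A reader might also infer that the IRB's look at the first 10 subjects would miss a calculable share of complaints after Tx3. The documents do not support a figure: they state neither the enrolment span nor the date of that look, and do not say that it draws on item 7 notices rather than the CRF. Only the missing cut-off can be noted.

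The Appendix G finding rests on the form's table as it appears in the document, which shows no further rows or columns.

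**What to change.** **SOP item 7.** State that:

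- it applies to any subject with a minor complication, whether or not she had a burn;
- sections 9.1.6 and 9.1.7 prevail where they require earlier notice;
- all other minor complications are reported before the subject's next treatment and in any case within 30 days;
- complaints after Tx3 are included before the first-10 results go to the IRB.

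Altered sensation should stay off the section 9.1.6 list, since adding it could remove the immediate notice under section 9.1.7. With that precedence rule, altered sensation read as unanticipated is notified at once, and the before-next-treatment deadline serves the other minor complications.

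**Appendix G.** Add a row for numbness or altered sensation lasting beyond the day of treatment, worded so that the brief tingling expected in section 7.6.1 is not counted. Add columns for day 5, day 6, more than 7 days (with date), and not resolved.

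**Cost.** One amendment, with no extra visits, staff or procedures. Paperwork for minor events is slightly faster, including a same-day notice when a complaint is first raised at a treatment visit, and the form is slightly longer.
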